In order to further evaluate the utility of DCR as a tool for assessment of baseline respiratory physiology, it is important to be able to compare it with real time conventional pulmonary function tests such as spirometry. Previous studies have compared sequential lung function testing to dynamic x-ray images; even if attempting a maximal effort there will be significant variability in 2 separate manoeuvres (i.e when sequentially performing a dynamic x-ray and then contiguously a spirometry). Currently there have been no studies which compare a dynamic chest x-ray with a simultaneous lung function study such as spirometry.

This study will therefore address this issue using performing simultaneous spirometry and DCR. Therefore one key aim of the study would be to establish how DCR compares with spirometry in a healthy population of individuals.

We would seek to also perform the DCR with simultaneous spirometry in a cohort of CF patients. DCR and spirometry are already performed as part of the annual review process. As highlighted DCR is generally well tolerated by pwCF. Spirometry can be physically or psychologically more challenging for pwCF. By performing simultaneous spirometry and DCR it would allow for a comparison with the healthy control group. This would provide the second aim of the Study to understand how we can relate DCR to pwCF's Spirometry.

Finally, as mentioned above DCR has become part of our annual review process in LHCH since 2019. The annual review process seeks to capture the clinically relevant information needed to assess the overall health of pwCF. By further analysing these DCR films with the other metrics of annual review process we may better understand how DCR relates to lung health over time. For example, are there any features of DCR which will predict future outcomes for pwCf. This study will therefore explore the relationship between longitudinal changes in DCR and key clinical measures of CF.

Aims:

1. Measure lung function via spirometry with simultaneous DCR in healthy controls
2. Measure lung function via spirometry with simultaneous DCR in pwCF
3. Investigate the relationship between spirometry and DCR in healthy controls, CF, and compare these two cohorts.
4. Investigate the relationship between DCR imaging and key clinical markers of CF recorded in the annual review process.

Null hypothesis: there is no relationship between parameters recorded by DCR and that of conventional spirometry in healthy individuals

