Subjects will perform spirometry in upright seated position which chest resting forward on the flat panel of the chest x-ray machine. The Spirometry instructions are given by a pulmonary physiologist who call out instructions. Spirometry requires a a deep inspiration followed by a maximal expiration into a hand held tube device. All pulmonary physiologists conducting the research at LHCH are accredited with the association for respiratory technology and physiology practioners(ARTP) and with the registration council for clinical physiologists (RCCP). The first 2 attempts will be spirometry only (as opposed to DCR). This is inline American Thoracic Society/European Respiratory Society repeatability and acceptability criteria (see below) and will allow a comparison with third spirometry attempt. The two non-DCR manoeuvres will facilitate volunteer comfort with the technique and allow for further coaching if required before the DCR image is captured. The third 'live' attempt will be recorded in conjunction with a DCR. The investigator tells the radiographer when to start recording the x-ray and breathing instructions are called out as per conventional Spirometry instructions.

All Spirometry will be reviewed by LHCH pulmonary physiologists and be entered on a clinical master datasheet. The following are the key Data points which will be recorded for the spirometry attempt with DCR (absolute and percentage predicted values):

- FEV1
- FVC
- FEV-1/FVC ratio

Table 3: ATS/ERS Repeatability and Acceptability Criteria

Spirometry	
Spirometry Within-Manoeuvre Criteria	Spirometry Between-Manoeuvre Criteria

*3x Acceptable flow volume loops performed free from significant artefact including;
Cough during first second of exhalation, Glottis closure that influences the measurement
Early termination or cut-off, Not maximal effort, Leak, Obstructed mouthpiece
Duration ≥ 6s or until a plateau in the volume-time curve or if the subject cannot or should not continue to exhale*

*The two largest values of FEV1 must be within 0.150L of each other
The two largest values of FVC must be within 0.150L of each other*

Dynamic Chest X-ray

Dynamic chest x-rays are performed in the x-ray room in Liverpool heart and chest Hospital. This is simultaneous with spirometry so will occur in the same place.

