A physical anatomical marker (left/right) is manually added to the detector. Density is set to -2 on the control panel, and the dynamic study function selected. The tube filter is set at 1.0mm Al, 0.1mmCu (copper and aluminium). The SID (distance to detector) is set to 200cm. A 180cm focal distance grid (40L per cm, ratio 12:1, and 17 by 17 inch / 42.18cm x 42.18cm) is used. Exposure factors are set at tube voltage 100kVP, tube current 80mA, exposure duration 4.0ms. Collimation (the adjustment of the x-ray field size to the minimum needed to capture the required images for a specific patient) is performed as per a standard chest x-ray, usually around 40cm by 30cm. The patient is positioned in a posterior-anterior position.

The frame rate for those participants undergoing routine clinical imaging will be set at 15 frames per second (fps), the standard frame rate used clinically.

Breathing instructions are called out as per Spirometry instructions. The image capture is stopped once the breathing the spirometry action is complete (this can be completed in around 10s or 150 frames), or if the 220 frame limit is reached, whichever comes first. If the spirometry is suboptimal the procedure cannot be repeated.

Once the image capture/spirometry is complete, exposure factors are recorded by the operator, including the total number of frames and total duration in seconds.

The images captured are transferred to the local PACS server as well as an NHS server. Images are then downloaded from the NHS server onto a secure workstation for analysis in the research department. Images are anonymised to comply with data protection policies. Images are then processed using Konica Minolta DI-X1 software and re-uploaded to the server.

The images acquired by the DCR are processed using the Di-X1 machine using the computer algorithms. Further updates to the machine may allow further analysis. Key quantitative measures derived from the D1-X1 analysis of the DCR currently include:

1. Diaphragmatic excursion – maximal inspiratory and expiratory in mm
2. Peak diaphragm velocity
3. Peak diaphragm velocity at inspiration / expiration
4. Peak distance from apex to diaphragm
5. Lung field area during range of maximal inspiration / expiration – as calculated by Konica Minolta software. Reviewed individually to ensure algorithm accurately detecting lung field area.

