- Current exacerbation

Spirometry exclusion criteria (same as for Group A, see above)

Statistical analysis

Statistical analysis will be carried using the R software package, produced and supported by the R Foundation for Statistical Computing, under the GNU GPL v2 public license.

All data will be collated electronically and stored on a secure server in line with data protection.

Two-sided P-values of <0.05 will be considered as statistically significant. Confidence intervals will be presented where appropriate and feasible.

Comparison of the data will be primarily between dynamic chest x-ray results and spirometry data. Depending on the distribution of the dataset, paired t-tests or the relevant non-parametric equivalent will be used to analyse within groups. Categorical data will be presented as frequency and percentage. Continuous data will be presented as number of observations, mean, standard deviation, median and interquartile range as appropriate.

Proposed timetable of events

- **December 2022** – Start of Protocol write up.
- **January 2023** – research proposal submission to local research committee
- **March 2023**- Sure group review and revisions to protocol and study literature
- **July 2023** -Iras application
- **September 2023 to September 2024** - Data collection is projected to take around 365 days, aiming for completion end of July 2023. This allows for the recruitment of 2 ‘healthy volunteers’ and 2 people with CF a week.
- **September to October 2024**- Data analysis
- **October/November/December 2024**- write up of research results +/- publication

Figure 3 – Gantt Chart of Projected Timetable December 2022 – December 2024

Task	D	J	F	M	A	M	J	J	A	S	O	N	D	J	F	M	A	M	J	J	A	S	O	N	D
Protocol Write up	█	█	█	█	█	█	█																		
R&I committee meeting LHCH		█																							
Sure Group review				█	█	█	█																		
Iras Application							█	█	█																
Study period										█	█	█	█	█	█	█	█	█	█	█	█	█	█	█	
Data analysis																						█	█		
Results write up																							█	█	█

Safety

Ionising Radiation

This study requires exposure to ionising radiation.

We are exposed to radiation in our daily lives and our annual average radiation exposure in the UK is 2.7mSv

An example of typical radiation doses from clinical investigations are included below.

Table 4 - Effective Doses for Common Radiological Examinations

Projection	Estimated effective dose (mSv)
Chest PA	0.014
Chest lateral	0.038

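### The analysis section names no method that estimates the DCR–spirometry relationship, no primary spirometry scale and no adjustment for height, sex or age, which limits what a correlation with litres, or a direct cohort comparison, can show

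*Combined protocol and SAP*

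**What the plan says.** Aim 3 is to "Investigate the relationship between spirometry and DCR in healthy controls, CF, and compare these two cohorts". The null hypothesis for the healthy cohort is that "there is no relationship between parameters recorded by DCR and that of conventional spirometry in healthy individuals"; the CF null is parallel, and both alternatives speak of correlation.

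The Statistical analysis section sets a two-sided 0.05 threshold and lists descriptive summaries. On inference it says "Comparison of the data will be primarily between dynamic chest x-ray results and spirometry data" and that, depending on distribution, "paired t-tests or the relevant non-parametric equivalent will be used to analyse within groups". It names no correlation or regression, no covariate and no method for comparing the cohorts.

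On the variables:
- Spirometry section: "The following are the key Data points which will be recorded for the spirometry attempt with DCR (absolute and percentage predicted values"), namely FEV1, FVC and their ratio. Neither scale is named as primary.
- Dynamic Chest X-ray section: the measures include diaphragm excursion, "maximal inspiratory and expiratory in mm", and "Lung field area during range of maximal inspiration / expiration". No indexing to body size is stated. The list is open: "Further updates to the machine may allow further analysis".
- Enrolment criteria: both cohorts are limited to ages 17–50. Height and sex are not named as recorded variables, covariates or matching factors.

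The Sample and Recruitment section calls the study exploratory and hypothesis generating, with no power calculation. Healthy volunteers come through hospital and university advertising, and people with CF through the annual review clinic. The target is 100 in each cohort.

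**The concern.** There are two linked gaps. The named test does not fit the question: a paired t-test of a DCR measure against a spirometry measure asks whether two means differ, and here they are in different units. Once a correlation is used instead, as the hypotheses imply, the plan does not say on which spirometry scale or with what adjustment.

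That choice affects interpretation. Larger people can have both larger DCR distances and areas and more litres. A correlation with litres then mixes two things: that DCR and spirometry both scale with the body, and that DCR follows lung function among people of similar size. The section on DCR as an assessment of pulmonary function raises possible use of DCR as a surrogate for some lung function parameters, and the second component bears on that. For the healthy-versus-CF comparison, a difference in DCR measures could partly reflect who was recruited if the cohorts turn out to differ in size, sex or age.

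**Working it through.** The plan gives no effect size, SD or power, so there is no figure of its own to reproduce. Inputs from the documents are n=100 per cohort and two-sided 0.05. Every size effect below is an assumption.

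**1. The named test.** With an assumed mean excursion of 40 or 60 mm and FEV1 of 3.2 L, the paired difference is 36.8 or 56.8 in mixed units. Simulated paired t-tests gave p<0.05 in 100% of studies at true r of 0, 0.4 and 0.8 alike. This is a units artefact; it shows only that the test carries no information on the relationship.

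**2. Correlation induced by size, litres scale.** Let DCR correlate with size at a (0.3–0.6) and spirometry at b (0.4–0.7), with no association at a given size. Then r = a × b.
- Low end: 0.3 × 0.4 = 0.12. High end: 0.6 × 0.7 = 0.42.
- Simulated chance of p<0.05 (6,000 replicates): 22.6–99.4%.

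**3. After adjustment.** If height, sex and age together capture a share k of the variance in size, the partial correlation is ab(1−k) / √[(1−a²k)(1−b²k)].
- k = 1: 0.00; p<0.05 in 4.8–5.2%.
- k = 0.8: 0.024/√(0.928 × 0.872) = 0.03, to 0.084/√(0.712 × 0.608) = 0.13; p<0.05 in 6.0–24.3%.
- k = 0.5: 0.06/√(0.955 × 0.92) = 0.06, to 0.21/√(0.82 × 0.755) = 0.27; p<0.05 in 9.8–77.5%.

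**4. % predicted scale, size fully removed from spirometry.** No relationship is induced, so p<0.05 occurs in 5%. A true association of 0.30 at a given size is diluted to 0.30 × √(1−a²): 0.29 at a = 0.3 and 0.24 at a = 0.6. By Fisher z with SE 1/√97, power is 83% and 67%, against 85% for the adjusted analysis with three covariates (SE 1/√94).

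**5. Aim 3 as a comparison of relationships.** Suppose CF adds 1–2 times the non-size variance of FEV1, with size acting equally in both cohorts. The DCR slope is then the same in both, but the raw correlations differ. At a = 0.6, b = 0.7 and twice the variance, r is 0.42 in controls and 0.42/√(1 + 2 × 0.51) = 0.30 in CF.
- Fisher z test of raw r between cohorts: p<0.05 in 5.2–17.2% across settings.
- DCR × cohort slope test in a pooled model: 4.2–5.6%, adjusted or not, including with a 0.5 SD size imbalance. I re-ran this and found it close to 5% in every setting.

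**6. Direct comparison of a DCR measure.** A size imbalance of d SD shifts the DCR mean by a × d SD; the SE is √(2/100) = 0.141.
- d = 0: 5.0–5.3%.
- d = 0.1: 5.6–6.9%.
- d = 0.2–0.5: shift 0.3 × 0.2 = 0.06 to 0.6 × 0.5 = 0.30 SD; p<0.05 in 6.9–55.7%.
- Adjusted, d = 0.2–0.5: 4.7–5.6% (k = 1), 5.0–7.5% (k = 0.8), 5.7–20.6% (k = 0.5).

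**7. Cost of adjustment.** The correlation detectable with 80% power is tanh(2.8016/√97) = 0.277 without covariates and tanh(2.8016/√94) = 0.281 with three.

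**The case against.** The case on the other side is substantial, and much of it stands.

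- The nulls say only that there is no relationship. A correlation arising through body size is a relationship, so a reader who infers an inflated type I error would be wrong. This stands; the 22.6–99.4% in step 2 are not false-positive rates.
- A reader might infer that the effect of size cannot be removed from the planned data. The documents do not support that: % predicted values are recorded and largely remove size from spirometry, and calculating them implies that height, sex and age are taken. The questionnaire and clinical data are not itemised, so their absence cannot be presumed. What remains is that no scale is given priority.
- Surrogate use is a tentative remark in the rationale and not one of the four aims. Adjusting for height changes the question asked, and the unadjusted association with litres is a legitimate quantity. This stands, and is why both should be reported.
- A reader might infer that Aim 3 fails without adjustment. Step 5 does not support that: the slope test held its error rate unadjusted. Only a test of raw correlations was inflated, and the plan does not name one.
- A reader might infer that the cohort comparison is confounded. The documents report no imbalance, and at 0.1 SD the effect is slight.
- The paired test could have another use, since the Spirometry section anticipates comparing the DCR-coupled attempt with the two before it. That would be a sound use, but the analysis section does not limit the test to it.

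None of this supplies a method for the stated aims.

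**Conclusion.** The point holds in a limited form. Followed as written, the Statistical analysis section would not estimate the relationship that the aims and hypotheses are about, and it gives no method for the cohort comparison in Aim 3. This follows from the text and needs no assumption.

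The body-size part concerns interpretation. A raw correlation with litres would say less than it appears to about whether DCR tracks lung function among people of similar size. That people of similar size are the relevant comparison for a surrogate claim is this review's reading; the documents set no such criterion. The direct cohort comparison is at risk only if the cohorts differ in size, sex or age. The documents neither report such a difference nor prevent one beyond the shared 17–50 age range.

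All magnitudes rest on assumed size correlations and imbalances and on a single shared size factor. The slope result also assumes that size acts equally in both cohorts. The figures show scale only. Severity is minor to moderate, because the study is declared exploratory.

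**What to change.** Before analysis, amend the Statistical analysis section as follows.

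- For the DCR–spirometry question, replace the paired t-test with correlation and regression. If the paired test is kept for comparing spirometry attempts, say so.
- Name the primary spirometry scale.
- In each cohort, report the unadjusted correlation beside the association of FEV1 or FVC in litres with the DCR measure adjusted for height, sex and age, both with 95% CIs. Give % predicted results as supportive. Rest any statement about surrogate use on the adjusted result.
- For Aim 3, fit a pooled model with cohort, DCR, DCR × cohort, height, sex and age, and compare slopes. Adjustment here serves interpretation and precision. As a sensitivity check, let the covariate slopes differ by cohort.
- Adjust any direct cohort comparison of DCR measures for the same three variables.
- Confirm that height, sex and age are kept in the analysis dataset. Report how much DCR and spirometry variance they explain, and state that size effects remain if they capture size poorly (step 3, k = 0.5).

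The cost is a few degrees of freedom (step 7) and some drafting. No extra visits, participants or imaging are needed, provided the three variables are retained.

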Null hypothesis: there is no relationship between variables recorded by dynamic chest x-ray and that calculated by spirometry in people with CF.

Alternative hypothesis: We can correlate the findings on DCR with that of recorded spirometry findings.

Alternative hypothesis: there is a correlation between dynamic chest x-ray and that calculated by Spirometry in people with CF

Funding

This Study has received no specific resources from any funding agency either public or commercial.

Konica Minolta have provided a grant in kind with the dynamic x-ray machine, workstation and imaging software and technical support. Konica Minolta does not have any input in the clinical acquisition of data from relevant patient group.

Method and analysis

Study Setting

Single centre study based at Liverpool Heart and Chest Hospital. From a practical perspective the best place for the study given:

1. Dynamic x-ray machine is novel and located on site here
2. Tertiary centre for adult cystic fibrosis.

Part A : Real-time paired DCR and Spirometry in Healthy control Group

Aim: Explore relationship between the Dynamic CXR imaging and simultaneous spirometry in a healthy population with no known underlying lung condition.

Study design: The study involves the recruitment of healthy volunteers from general population. We would aim to recruit n=100 participants. The key investigations are Dynamic chest x-ray and paired spirometry as outlined below. Individuals will be recruited through a poster campaign successful in previous studies

Part B: Real-time paired DCR and spirometry in a CF subgroup.

Aim: Explore relationship between the Dynamic CXR imaging and simultaneous spirometry in a CF population

Study Design: This aspect of the study involves recruitment pwCF to perform DCR with paired spirometry, aiming to recruit n= 100 people. The above format would be repeated with paired spirometry and DCR in CF subgroup of LHCH patients. CF patients at LHCH attend a once yearly review process called annual review. The current format already includes a dynamic chest x-ray and spirometry as part of this Process (although not simultaneous). Through CF data base co-ordinator, a letter will be provided to all pwCF if interested.

This would allow for a Direct comparison of spirometry with DCR data. Furthermore, it therefore also allows for a comparison of Comparison with the control group. The structure of how these investigations are performed is outlined below.

Part C:

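### The only inferential method named, a paired test within groups, cannot test the plan's no-association nulls, compare the two cohorts (Aim 3) or relate DCR to clinical markers (Aim 4 / Part C)

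*Combined protocol and SAP*

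**What the plan says.** The hypotheses follow the list of aims, one pair per cohort, and all concern association. For healthy volunteers the plan states: "Null hypothesis: there is no relationship between parameters recorded by DCR and that of conventional spirometry in healthy individuals". The null for people with cystic fibrosis (CF) has the same form, and its alternative is that "there is a correlation between dynamic chest x-ray and that calculated by Spirometry in people with CF".

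Two aims go further. Aim 3 is to "Investigate the relationship between spirometry and DCR in healthy controls, CF, and compare these two cohorts". Aim 4 is to "Investigate the relationship between DCR imaging and key clinical markers of CF recorded in the annual review process". The rationale adds that the study will "explore the relationship between longitudinal changes in DCR and key clinical measures of CF". Part C covers both: its aim refers to change in DCR and its design paragraph to baseline DCR.

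The Statistical analysis section says: "Comparison of the data will be primarily between dynamic chest x-ray results and spirometry data". The next sentence gives the only inferential method: "paired t-tests or the relevant non-parametric equivalent will be used to analyse within groups". The rest of the section covers software, data storage, a two-sided 0.05 threshold, confidence intervals where feasible, and descriptive summaries. No section names a correlation coefficient, a regression, a between-cohort test or a model for repeated measures.

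**The concern.** A paired t-test, or its signed-rank counterpart, asks whether two measurements on the same people differ on average. The hypotheses ask whether people with larger DCR values also have larger spirometry values. Two variables can have equal means and be strongly related, or different means and be unrelated, so one result says nothing about the other.

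A paired test within a group also cannot compare two independent cohorts. Nor can it relate DCR to a clinical marker: applied to two DCR films it would show whether DCR changed, but not whether that change goes with a clinical change.

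The plan therefore sets a significance threshold but names no test that could reject either null, and none for Aims 3 and 4. The analyst would have to choose the method after the data are in, and also which DCR–spirometry pair to emphasise. The Dynamic Chest X-ray section lists five kinds of DCR measure and the Spirometry section three spirometry values, so there are 5 × 3 = 15 possible pairs per cohort, before splitting by inspiration and expiration or by absolute and percentage predicted values.

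**Working it through.** The plan has no power or precision figure to reproduce; Sample and Recruitment says no power calculation was made.

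**1. Aim against method**

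| Question in the plan | What is needed | Can a within-group paired test supply it? |
|---|---|---|
| Null of no association, healthy | Test or estimate of association | No |
| Null of no association, CF | Same | No |
| Aim 3, cohort comparison | Comparison of two independent groups | No |
| Aim 4 / Part C, DCR and clinical markers | Association, with repeated measures where they occur | No |
| Spirometry attempts 1–2 against attempt 3 | Within-person difference, same unit | Yes |

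**2. Response of each test to association**

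Inputs: n = 100 (recruitment target, Parts A and B) and two-sided 0.05 (Statistical analysis). Assumptions: bivariate normal data, SD 1 for each variable, 3,000 simulated datasets per setting.

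| True r | Mean shift | Paired t rejects | Wilcoxon signed-rank rejects | Pearson rejects |
|---|---|---|---|---|
| 0 | 0 | 5.6% | 5.5% | 5.5% |
| 0.3 | 0 | 4.8% | 4.7% | 87% |
| 0.6 | 0 | 4.8% | 4.7% | 100% |
| 0.9 | 0 | 4.8% | 4.8% | 100% |
| 0 | 0.5 SD | 94% | 93% | 4.7% |

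Check of the last row: at r = 0 the SD of the difference is √2, so the non-centrality is (0.5/√2) × √100 = 3.54. The power of the paired t-test is then 93.8%, which agrees.

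**3. Precision of a matching analysis**

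95% CI for r: tanh(atanh(r) ± 1.96/√(n−3)). At r = 0.5 and n = 100 this is tanh(0.549 ± 0.199) = 0.34 to 0.63.

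Smallest r with 80% power: tanh(2.802/√(n−3)) = tanh(0.2845) = 0.28 at n = 100.

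The target of 100 may not all be evaluable, because a suboptimal DCR manoeuvre cannot be repeated. Assumed lower numbers give:

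| Evaluable n per cohort | 95% CI at r = 0.5 | Smallest r, 80% power |
|---|---|---|
| 100 | 0.34 to 0.63 | 0.28 |
| 80 | 0.31 to 0.65 | 0.31 |
| 60 | 0.28 to 0.67 | 0.35 |

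**4. Aim 3: slopes and correlations are different questions**

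Comparing two correlations, the smallest Fisher z difference with 80% power is 2.802 × √(2/97) = 0.40, for example 0.50 against 0.15.

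Next, assume equal slopes in both cohorts, r = 0.5 in controls and n = 100 each (20,000 simulated datasets per setting). SDs are relative to controls; the documents give none.

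| CF DCR SD | CF residual SD | True CF r | Fisher z rejects | Ordinary interaction rejects | Interaction, unequal variances, rejects |
|---|---|---|---|---|---|
| 1.5 | 1 | 0.655 | 37% | 5% | 5% |
| 2 | 2 | 0.50 | 5% | 1.5% | 5% |
| 0.5 | 2 | 0.143 | 80% | 9.6% | 5% |

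In rows 1 and 3 the correlations truly differ although the slopes do not. The ordinary interaction test holds its 5% level only when residual variances are equal or nearly so; standard errors that allow unequal variance restore it in these settings.

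**The case against.** The strongest reply is that this is an omission in an exploratory study whose intent is plain. The first alternative hypothesis says "We can correlate the findings on DCR with that of recorded spirometry findings", Sample and Recruitment calls the work hypothesis generating, and the statistical section does not say that paired tests are the only tests or that they test the nulls. All of this is true. It shows that the investigators have correlation in mind, and it excuses the missing power calculation. It does not supply a method: the hypotheses express intent, while the section that should turn intent into analysis names a different test directly after declaring the main comparison. If the paired tests are meant only for spirometry attempts 1–2 against attempt 3, the main comparison and Aims 3 and 4 have no test at all.

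A reader might infer from the two adjacent sentences that the plan will test millimetres of diaphragm excursion against litres, with a result that depends on the units. No section says so, and any rejection rate would rest on assumed means and SDs. The point does not need that reading.

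A reader might also take the 37% and 80% for Fisher z as false positives. They are not: the correlations differ in those settings, and the plan does not say whether Aim 3 concerns slopes or correlations.

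Finally, the 15 possible pairs show how much is left open. The plan lists the measures but does not commit to testing every pair.

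**Conclusion.** The point stands and should be corrected before analysis. Following the one named method would leave both stated nulls, Aim 3 and Aim 4 / Part C untested. This follows from what a paired test measures and depends on no assumed trial value; the simulated rates (about 5% at any correlation with equal means, 94% at zero correlation with a 0.5 SD shift) only illustrate it under normality with n = 100.

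It does not follow that the design or data are at fault. The paired DCR and spirometry records are what a correlation or regression needs, and at the target size they would support useful estimates. The precision figures assume that all 100 per cohort are evaluable and that the Fisher z approximation holds; the 80 and 60 rows show the loss if fewer are.

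**What to change.** Amend the Statistical analysis section before the data are analysed:

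1. **Paired tests.** Restrict them to same-unit, within-person comparisons, such as spirometry attempts 1–2 against attempt 3, and name the variables.
2. **Within each cohort.** Use Pearson or Spearman correlation and/or linear regression of FEV1, FVC and FEV1/FVC on each DCR measure, with 95% CIs. Ideally the investigators name one main pair in advance and label the rest exploratory. Diaphragm motion with vital capacity or FEV1 has support in the section on previous work, but that evidence comes only from healthy volunteers without CF.
3. **Aim 3.** State whether slopes or correlations are compared. For slopes, use a DCR-by-cohort interaction with standard errors that allow unequal residual variance.
4. **Aim 4 / Part C.** List the clinical markers, then regress them on baseline DCR and on within-patient change in DCR, with a patient random effect where annual measures repeat. Part B notes that routine annual-review DCR is not simultaneous with spirometry, whereas the study film is taken during a spirometry manoeuvre. Analyse the study film separately or flag it in the model.

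The cost is some wording, a few decisions by the investigators and a little more analysis. No new data, participants or procedures are needed.
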